2.2 Treatment Assignment

All participants will be centrally randomized using an Interactive Response Technology (IRT). Before the study is initiated, each user will receive log-in information and directions on how to access the IRT. After the participant's initial eligibility is established and informed consent has been obtained, the participant must be enrolled into the study by calling an IRT to obtain the participant number. Every participant who signs the informed consent form must be assigned a participant number in IRT. The investigator or designee will register the participant for enrollment by following the enrollment procedures established by BMS. The following information is required for enrollment:

- Date that informed consent was obtained
- Year of birth
- Gender at birth

Once enrolled in IRT, enrolled participants who have met all eligibility criteria will be ready to be randomized through the IRT. The following information is required for participant randomization:

- Participant number

- Year of birth
- PD-L1 status (PD-L1 positive vs. PD-L1 negative/indeterminate) entered by vendor
- BRAF V600 mutational status
- M (Metastatic) Stage at screening

Participants meeting all eligibility criteria will be randomized in a 1:1 ratio and stratified by PD-L1 status, BRAF status, and AJCC M stage as described below:

- PD-L1 status
 - PD-L1 positive ($\geq 1\%$ tumor cell membrane staining in a minimum of 100 evaluable tumor cells) vs.
 - PD-L1 negative ($< 1\%$ tumor cell membrane staining in a minimum of 100 evaluable tumor cells) / indeterminate (tumor cell membrane scoring hampered by high cytoplasmic staining or melanin content)
- *BRAF* mutational status
 - BRAF V600 mutation positive vs.
 - BRAF V600 wild type
- AJCC M stage at screening
 - M0/M1a(0)/M1b(0) vs.
 - M1a(1)/M1b(1)/M1c(any)/M1d(any)

The randomization procedures will be carried out via permuted blocks within each stratum, defined by combination of PD-L1 status (positive, negative/indeterminate), BRAF V600 mutational status (BRAF mutated, BRAF wild type), and M Stage (M0/M1a(0)/M1b(0), M1a(1)/M1b(1)/M1c(any)/M1d[any]). The exact procedures for using the IRT will be detailed in the IRT manual.

2.3 Blinding and Unblinding

Treatment allocation will be unblinded upon approval of Revised Protocol 01 and a list of treatment assignments for each subject will be provided to each site with randomized subjects.

2.4 Protocol Amendments

Revised Protocol 01 on 13-Jun-2018.

2.5 Data Monitoring Committee

NA.

3 OBJECTIVES

Not applicable per Revised Protocol 01.

3.1.1 Safety

Safety will be analyzed through the incidence of deaths, adverse events, serious adverse events, adverse events leading to discontinuation, adverse events leading to dose modification, and specific laboratory abnormalities (worst grade) in each treatment arm. Toxicities will be graded using the National Cancer Institute (NCI) Common Terminology Criteria for Adverse Events (CTCAE) version 4.03.

4 ENDPOINTS

[REDACTED]

[REDACTED]

[REDACTED]

[REDACTED]

[REDACTED]

5 SAMPLE SIZE AND POWER

NA.

6 STUDY PERIODS, TREATMENT REGIMENS AND POPULATIONS FOR ANALYSES

6.1 Study Periods

6.1.1 *Baseline Period*

Baseline evaluations or events will be defined as evaluations or events that occur before the date and time of the first dose of study treatment. Evaluations on the same date and time of the first dose of study treatment will be considered as baseline evaluations. For subjects who are randomized but not treated, baseline evaluation will be defined as those that occur before the date and time of randomization.

In cases where the time (onset time of event or evaluation time and dosing time) is missing or not collected, the following definitions will apply:

- Pre-treatment AEs will be defined as AEs with an onset date prior to but not including the day of the first dose of study treatment
- Baseline evaluations (laboratory tests, pulse oximetry and vital signs) will be defined as evaluations with a date on or prior to the day of first dose of study treatment

If there are multiple valid assessments, the assessment that is closest to day (and time if collected) of the first dose of study treatment will be used as the baseline in the analyses. If multiple assessments are collected at the same date (and time if collected), the assessment with the latest database entry date (and time if collected) will be considered as baseline.

6.1.2 *Post Baseline Period*

On-treatment AEs will be defined as AEs with an onset date-time on or after the date-time of the first dose of study treatment (or with an onset date on or after the day of first dose of study treatment if time is not collected or is missing). An AE will be counted as on-treatment if the event occurred within 30 days (or 100 days depending on analysis) of the last dose of study treatment.

On-treatment evaluations (laboratory tests, pulse oximetry, and vital signs) will be defined as evaluations taken after the day (and time, if collected and not missing) of first dose of study

treatment. An evaluation will be counted as on-treatment if it occurred within a safety window of 30 days (or 100 days depending on analysis) of the last dose of study treatment.

Late emergent drug-related AEs will be defined as drug-related AEs with an onset date greater than 100 days after the last dose of study treatment in subjects who are off study treatment.

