**Duration:**

As of 19-Apr-2018, enrollment in the study was closed. Participants currently enrolled in the study may continue to receive treatment until progression, unacceptable toxicity, withdrawal of consent, or 104 weeks from the first dose of nivolumab.

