**Figure 5.1-1: Study Design Schematic**

Note: As of Revised Protocol 01, treatment will no longer be blinded, and participants in Arm B will no longer receive BMS-986205 Placebo. Participants in Arm A, have the option to discontinue BMS-986205, and continue nivolumab monotherapy, at investigator discretion.

A pre-treatment tumor sample to determine PD-L1 status is required to be submitted from all participants prior to randomization. The sample must be obtained within 3 months prior to enrollment from a metastatic tumor lesion or from an unresectable primary tumor lesion. The tumor sample must be taken from a site of disease which has not been previously irradiated. In

addition, no intervening treatment may have been administered between the time of biopsy/surgery and randomization. Pre-treatment tumor tissue biopsy specimens in the form of a paraffin-embedded block or, optimally, at least 20 unstained slides, will be requested; a minimum of 10 slides is required. The pre-treatment tumor sample must be a core biopsy, punch biopsy, excisional biopsy, or surgical specimen; fine needle aspiration samples and cytology samples are not acceptable. If sufficient tissue is not available from within 3 months prior to enrollment, then a fresh biopsy will be required during the screening period. Samples will be submitted to the analytical laboratory for PD-L1 testing. The analytical laboratory must provide IRT with confirmation of the related results prior to randomization.

Participants must have a documented BRAF status prior to randomization. Those participants enrolling in this study without documented results must have testing performed locally and results (wild type or mutant) be available prior to randomization. Participants with indeterminate or unknown BRAF status results will not be permitted to randomize to a treatment arm.

During the treatment phase, adult participants will receive:

- Arm A: BMS-986205 100 mg PO QD and Nivolumab 480 mg IV Q4W for up to 104 weeks (approximately 2 years). Under Revised Protocol 01 investigators have the option of continuing participants on nivolumab monotherapy.
- Arm B: Nivolumab 480 mg IV Q4W for up to 104 weeks (approximately 2 years). Under Revised Protocol 01 BMS-986205 Placebo should not be administered.

One cycle of treatment is defined as 4 weeks.

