## **7 TREATMENT**

Study treatment is defined as any investigational treatment(s), marketed product(s), placebo or medical device intended to be administered to a study participant according to the study randomization or treatment allocation.

An investigational product, also known as investigational medicinal product in some regions, is defined as a pharmaceutical form of an active substance or placebo being tested or used as a reference in a clinical study, including products already with a marketing authorization but used or assembled (formulated or packaged) differently than the authorized form, or used for an unauthorized indication, or when used to gain further information about the authorized form.

Other medications used as support or escape medication for preventative, diagnostic, or therapeutic reasons, as components of the standard of care for a given diagnosis, may be considered as non-investigational products.

Investigational products (IP) used in this trial are provided in [Table 7-1](#). There are no non-investigational products in this study.

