### 7.1.1 BMS-986205 Dosing

**Per Revised Protocol 01, treatment assignment will be unblinded and participants in Arm B will be discontinued from BMS-986205 Placebo. Participants in Arm A, may at the discretion of the investigator, discontinue BMS-986205, and continue on nivolumab monotherapy.**

For participants in Arm A that continue on BMS-986205, a bottle of BMS-986205 should be dispensed at each Day 1 visit within a cycle. Participants should be instructed that BMS-986205 should be administered once a day (approximately 24 hours apart) following a meal. The tablet must administered by mouth, swallowed whole, and not be crushed, chewed, dissolved or altered in any way.

Participants in Arm A that continue taking BMS-986205 should be provided with pill diaries at each visit and instructed to record intake of BMS-986205 in the diary after each daily administration.

BMS-986205 will be administered on an out-patient basis. Additional information on study drug preparation, handling and administration can be found in the Pharmacy Manual.

Participants should receive BMS-986205 until progression, unacceptable toxicity, withdrawal of consent by the participant, or completion of 104 weeks of treatment, whichever occurs first. Participants should begin study treatment within 3 calendar days of randomization.

Doses of BMS-986205 may be modified, interrupted or discontinued depending on how well the participant tolerates the treatment (See [Section 7.4.2](#) [modification], [Section 7.4.3](#) [delay], and [Section 8.1.1](#) [discontinuation]). If the dose of BMS-986205 is reduced, escalation will not be permitted. Skipped doses during interruptions should not be administered within the same cycle.

If nivolumab dosing is delayed for reasons other than study drug toxicity (eg, administrative issues, holidays, etc), BMS-986205 dosing should continue uninterrupted.

For details on prepared drug storage, preparation, and administration, please refer to the BMS-986205 IB and/or pharmacy binder. The selection and timing of dose for each participant is provided in [Table 7.1-1](#).

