### **7.1.2 Nivolumab Dosing**

Participants 18 years of age and older, or age of majority, should receive nivolumab at a dose of 480 mg as a 30-minute infusion on Day 1 of each treatment cycle until progression, unacceptable toxicity, withdrawal of consent/assent, or completion of 104 weeks of treatment, whichever occurs first.

Participants should begin study treatment within 3 calendar days of randomization

The dose of BMS-986205 (for participants in Arm A that continue receiving BMS-986205) should be given before the dose of nivolumab, but specific timing is not required. Participants should begin study treatment within 3 calendar days of randomization.

There will be no dose escalations or reductions of nivolumab allowed. For Q4W dosing cycles, participants may be dosed within a  $\pm 3$  day window. For this dosing cycle, participants may be dosed no less than 25 days and no more than 31 days between doses. In extenuating circumstances in which the participant cannot make the dosing schedule within the 3-day window, the BMS Medical Monitor/designee should be contacted.

Premedication is not recommended for the first dose of nivolumab.

Participants should be carefully monitored for infusion reactions during nivolumab administration. After the first nivolumab infusion, subjects should be monitored per local/institutional guidelines. If no such guidelines exist, an observation period of 2 hours after the end of the nivolumab infusion is suggested.

If an acute infusion reaction is noted, participants should be managed according to [Section 7.7.5](#).

Doses of nivolumab may be interrupted, delayed, or discontinued depending on how well the participant tolerates the treatment. Dosing visits are not skipped, only delayed.

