7.5.2 Serious Adverse Events

Serious adverse events will be summarized by treatment group:

- Overall summary of SAEs by worst CTC grade (any grade, grade 3-4, grade 5) presented by SOC/PT.
- Overall summary of drug-related SAEs by worst CTC grade (any grade, grade 3-4, grade 5) presented by SOC/PT.

All analyses will be conducted using the 30-day safety window.

A by-subject SAE listing will be provided for the “enrolled subjects” population.

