7.5.4 Adverse Events

Adverse events will be summarized by treatment group.

The following analyses will be conducted using the 30 days safety window:

- Overall summary of any AEs by worst CTC grade (1, 2, 3, 4, 5, not reported, total) presented by SOC/PT.
- Overall summary of drug-related AEs by worst CTC grade (any grade, grade 3-4, grade 5) presented by SOC/PT.

A by-subject AE listing will be provided.

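### After placebo withdrawal, the 30-day on-treatment window can close up to about 27 days later after the last infusion in Arm A than in Arm B, which tends to raise the Arm A AE and SAE percentages

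*SAP*

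**What the plan says.** SAP 6.1.2 (under 6.1 Study Periods) has an AE "counted as on-treatment if the event occurred within 30 days (or 100 days depending on analysis) of the last dose of study treatment". It names neither drug. Two sections then choose the 30-day version for the summaries by treatment group:

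- SAP 7.5.2, SAEs: "All analyses will be conducted using the 30-day safety window".
- SAP 7.5.4, AEs: "The following analyses will be conducted using the 30 days safety window".

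The protocol settles which doses count. Section 7 states: "Study treatment is defined as any investigational treatment(s), marketed product(s), placebo or medical device intended to be administered to a study participant". Tablets (active or placebo) and infusions are therefore all study treatment. SAP 6.3 agrees, since it counts placebo doses when it defines the treated population.

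Nivolumab is given on Day 1 of each four-week cycle in both arms (Protocol 7.1.2), and BMS-986205 is taken daily (Protocol 7.1.1). For Arm B, Protocol 5.1 adds: "Under Revised Protocol 01 BMS-986205 Placebo should not be administered". Arm A participants may stay on BMS-986205 or go on with nivolumab alone, at the investigator's discretion.

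**The concern.** Under double-blind dosing, both arms took a daily tablet, so the window started from the same kind of dose in each arm. Revised Protocol 01 changed that. In Arm B the last dose is now an infusion. In an Arm A participant still on BMS-986205 it can be a tablet taken almost four weeks after the last infusion. Two participants with identical infusions can then be followed for different lengths of time in the same table.

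The difference runs one way. The last dose of any component can never precede the last infusion, so for the same infusions the Arm A window is as long as the Arm B window or longer. A longer window can only add events, so the Arm A percentage tends to rise with no difference in toxicity.

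Efficacy analyses have been dropped, so the AE and SAE summaries by arm are the main output left. Readers will compare the two columns.

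**Working it through.** The plan gives no figure of its own to reproduce here. The check is calendar arithmetic on the protocol's schedule, followed by an illustration on assumed event rates.

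**Step 1. Gap on schedule.** Inputs: 28-day cycles, infusion on Day 1, tablets on Days 1 to 28, 30-day window. After k cycles:

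- last infusion = day 28(k − 1) + 1
- last tablet = day 28k
- gap = 28k − [28(k − 1) + 1] = 27 days, for any k

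The protocol synopsis ends treatment at "104 weeks from the first dose of nivolumab", which is 26 cycles. The last infusion is on day 28 × 25 + 1 = 701 and the last tablet on day 728. The window closes on 701 + 30 = day 731 in Arm B and on 728 + 30 = day 758 in Arm A on tablets. Arm A counts events up to 57 days after the last infusion, and Arm B up to 30.

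**Step 2. When the gap differs.**

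- Both drugs stop at the next Day 1 visit: the full 27 days. The full gap is therefore not confined to 104-week completers.
- Both drugs stop mid-cycle: smaller. Protocol 8.1 has tablets stop when nivolumab is discontinued.
- Treatment ended before placebo withdrawal, or tablets were dropped before a later infusion: zero.
- Infusion interval at its limits: Protocol 7.1.2 says "participants may be dosed no less than 25 days and no more than 31 days between doses". If the last tablet falls the day before the next infusion is due, the gap is 24 to 30 days.
- Infusion delayed for other reasons: Protocol 7.1.1 says "If nivolumab dosing is delayed for reasons other than study drug toxicity (eg, administrative issues, holidays, etc), BMS-986205 dosing should continue uninterrupted". The gap then exceeds the on-schedule value only if no later infusion is given, which should be rare.

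**Step 3. Illustrative effect on a percentage.** Let T be the days from first to last infusion, g the gap, and p the Arm B incidence. With a constant hazard:

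Arm A incidence = 1 − (1 − p)^[(T + g + 30)/(T + 30)]

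Assume p = 30% and g = 27. The arm-level excess is f times the excess among affected participants. Here f is the affected share of Arm A, and all others are taken to have the Arm B window.

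| T (days) | Window ratio | Arm A incidence | Excess, affected | Arm level, f = 25% | Arm level, f = 50% |
|---|---|---|---|---|---|
| 168 | 225/198 = 1.14 | 33.3% | +3.3 | +0.8 | +1.7 |
| 336 | 393/366 = 1.07 | 31.8% | +1.8 | +0.5 | +0.9 |
| 700 | 757/730 = 1.04 | 30.9% | +0.9 | +0.2 | +0.5 |

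Much shorter courses are left out on calendar grounds. Enrollment closed on 19-Apr-2018 and Revised Protocol 01 is dated 13-Jun-2018, with local approval still to follow. For short courses to have ended after placebo withdrawal, first dosing would have to fall close to the end of enrollment.

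**Step 4. Sensitivity (excess among affected, T = 168, 336, 700).**

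- 14-day gap: +1.7, +0.9, +0.5.
- First events cluster early (hazard after day 84 assumed one quarter of that before): replace t by H(t) = min(t, 84) + max(t − 84, 0)/4. For T = 168, H(225)/H(198) = 119.25/112.5 = 1.06. The excess is +1.5, +1.1, +0.7. At arm level this is +0.4, +0.3, +0.2 for f = 25% and +0.7, +0.5, +0.3 for f = 50%.
- Arm B incidence 10%: +1.3, +0.7, +0.3. Incidence 60%: +4.7, +2.6, +1.3 (both constant hazard, 27-day gap).

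**The case against.** The best defence is that the rule does what an on-treatment rule should do. A participant still taking BMS-986205 in those four weeks is exposed to an investigational drug, and events then belong in an on-treatment summary. That stands, and it is why the current tables should stay. It does not make the two columns comparable for the period after the last infusion.

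Second, the tables are descriptive. The SAP lists its objectives as not applicable and plans a synoptic report, and no test between arms is visible. Listings give dosing dates and individual events, so cases can be traced. This limits the consequence, but listings do not correct the percentages in the tables.

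Three stronger readings are tempting, and the documents do not support them.

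- A reader might infer that the anchor is undefined because SAP 6.1.2 names no drug. Protocol 7 and SAP 6.3 settle it, so naming it would be a clarification only.
- A reader might infer that nothing anywhere discloses the asymmetry. Only the visible SAP text is silent. Parts of the SAP are redacted, and the table mock-ups are in a Data Presentation Plan that is not among the documents.
- A reader might infer a large bias from short courses of treatment. That would need affected participants first dosed near the end of enrollment, and nothing in the documents shows how many there were.

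**Conclusion.** The point holds as a minor one. Revised Protocol 01 turned a symmetric window into one that depends on the arm, and the visible SAP text does not deal with this. The 27-day on-schedule gap follows from the protocol's schedule and its definition of study treatment, and needs no further assumption.

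The effect on the percentages cannot be computed, because the documents give neither the share of Arm A still on tablets after placebo withdrawal nor the local approval dates. With 30% incidence in Arm B, a constant hazard and the full gap, it is about +0.9 to +3.3 points among affected participants. At arm level it is about +0.2 to +1.7 points, if 25% to 50% of Arm A is affected. Early clustering of events or mid-cycle stops make it smaller, and a higher incidence can make it larger. The direction is towards Arm A throughout. This does not show that an observed excess in Arm A would be an artefact, only that a small part of one could be.

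**What to change.** 1. Keep the current tables in SAP 7.5.2 and 7.5.4 as the within-arm on-treatment summary. Add a footnote that, after placebo withdrawal, the window can run longer after the last infusion in Arm A than in Arm B.
2. Add one supplementary by-arm AE table and one SAE table whose window closes the same number of days after the last nivolumab infusion in both arms. The 100 days that SAP 6.1.2 already names would serve, because they cover 30 days after the last on-schedule tablet (27 + 30 = 57). For a 104-week completer both windows would then close on day 701 + 100 = 801.
3. Footnote the limits of these tables. They equalise only the post-infusion tail. They do not equalise treatment duration, the per-cycle methemoglobin testing of participants on BMS-986205, or open-label reporting. They include time on new therapy, and SAE collection narrows once new anti-neoplastic therapy starts (Protocol 9.2.1).
4. As a clarification only, state in SAP 6.1.2 that the anchor is the later of the last tablet and the last infusion.

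The cost is a sentence, the footnotes, one derived flag and two tables. No new data are needed. Protocol 9.2.2 and Table 2-3 already provide for at least 100 days of follow-up after study treatment, and the last infusion is never later than the last dose. The price is a window that counts events further from exposure. After a long infusion delay, some Arm A events soon after the last tablet would also appear only in the within-arm table.

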6.2 Treatment Regimens

The treatment group “**as randomized**” will be retrieved from the IRT system.

- Arm A: BMS-986205 100 mg PO QD and Nivolumab 480mg IV Q4W
- Arm B: BMS-986205 Placebo PO QD and Nivolumab 480mg IV Q4W

The treatment group “**as treated**” will be the same as the arm as randomized by IRT. However, if a participant received the incorrect drug for **the entire period** of treatment, the participant’s treatment group will be defined as the incorrect drug the participant actually received.

